7.2 RT Treatment management

Delays in radiation therapy occur for a variety of reasons (e.g. holidays, equipment issues, weather, etc.). Treatment interruptions of radiation therapy are discouraged but may be necessitated by acute complications. The reason for and duration of any such interruption must be documented. **A minimum of 4 daily radiation therapy treatments are required in any given week.** Any missed radiation treatments will be made up at the end of the treatment schedule such that the total number of delivered 1.8 Gy fractions remains 28.

During this study, if chemotherapy is held, radiation therapy will continue. If radiation is held, capecitabine will also be held; however, treatment with IPdR will continue unless otherwise contraindicated. Radiation may be held for grade 3 dermatitis radiation, grade 4 neutropenia, or other radiation-associated toxicity > grade 3 by CTCAE v5.0 at the discretion of the treating radiation oncologist. Radiation should be restarted subsequent to recovery at the discretion of the radiation oncologist consistent with standard practice.

7.2.1 Management of capecitabine for delay in radiation therapy

Capecitabine is administered BID on each day that the patient receives radiation treatment. If radiation therapy is held, no capecitabine is administered on that day. If the patient has taken the

AM capecitabine dose prior to arrival for radiation therapy, that is allowed, and the PM dose would be held. The patient should resume the AM capecitabine dose on the morning of the next scheduled radiation therapy appointment.

The duration of radiation therapy will be extended so that the total number of delivered fractions is 28 (Section 6.1). The patient should receive a minimum of 56 doses of capecitabine (BID on each day of radiation therapy and additional doses if an AM dose was taken prior to cancellation of radiation therapy for a given day).

7.2.2 Management of IPdR for delay in radiation therapy

IPdR is administered either once daily or twice daily, 7 days a week, beginning with the first dose of capecitabine on Day 1. IPdR must be taken 7 days/week for the duration of radiation therapy (*i.e.* to be discontinued only following the final dose of radiation therapy). If radiation therapy is held, IPdR continues unless criteria for dose adjustment is met per Section 6.2. IPdR either once daily or twice daily, 7 days a week, will continue through the last dose of radiation therapy. Patients may receive up to 5 additional days (10 doses) of IPdR to accommodate delays in radiation therapy.

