- a “moderate” toxicity, two additional patients will be entered at this dose level, and if
 - one of these patients develops a DLT, the stop/switch rule is invoked, and part IB commences
 - one of these patients develops a “moderate” toxicity, the stop/switch rule is invoked, and part IB commences
 - neither of the two additional patients develops a DLT or “moderate” toxicity, part IA recommences at the next dose level

A patient will be considered unevaluable if they receive $<67\%$ of their total intended dose of any study treatment (IPdR, capecitabine, or RT) for non-protocol required reasons. Patient medication diaries and RT documentation will be reviewed as each patient comes off-study to determine the actual total doses of each study treatment they received. If a patient is deemed unevaluable by this definition, they will be replaced by a new patient to be treated at the same intended dose level.

Part IA dose escalation schema			
Dose Level	Total radiation Gy (45 Gy primary field, 5.4 Gy [contact] Gy/fraction/day)	Capecitabine (mg/m² BID)	IPdR (mg BID) Administered throughout radiation
1A	50.4	825 mg/m ² BID	75 mg BID
2A	50.4	825 mg/m ² BID	150 mg BID
3A	50.4	825 mg/m ² BID	300 mg BID
4A	50.4	825 mg/m ² BID	600 mg BID
5A	50.4	825 mg/m ² BID	1,200 mg BID

BID – Twice Daily, RT – Radiation therapy

Part IA is closed to further accrual.

Part IB:

Under Part IB of this protocol, cohorts of 3-6 patients will be entered per dose level. In Part IB, 3 patients will initially be accrued to a dose level. If 0 of 3 patients do not experience grade 3 non-hematopoietic or grade 4 hematopoietic/GI DLT, then dose escalation will proceed. If a DLT is observed in one of the first 3 patients in a dose level cohort, the cohort will be expanded to a maximum of 6 patients.

Part IB dose escalation schema			
Dose Level	Total radiation Gy (45 Gy primary field, 5.4 Gy [contact] Gy/fraction/day)	Capecitabine (mg/m² BID)	IPdR (mg QD) Administered throughout radiation^{1,2}
1B	50.4	825 mg/m ² BID	75mg QD
2B	50.4	825 mg/m ² BID	150mg QD
3B	50.4	825 mg/m ² BID	300mg QD
4B	50.4	825 mg/m ² BID	600mg QD
5B	50.4	825 mg/m ² BID	1200mg QD
6B	50.4	825 mg/m ² BID	1800mg QD
7B	50.4	825 mg/m ² BID	2400mg QD

QD – Once Daily, BID – Twice Daily, RT – Radiation therapy

¹ The maximum allowed dose of IPdR is 2,400mg QD

² Actual doses will be rounded to account for availability of only 75 mg and 600 mg IPdR capsules

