6.1.2 IPdR administration

- Method of delivery is by oral administration in capsule form BID × 38 days for Part IA and once daily for Part IB (Week 6).
- Dosing will be based on the patient's assigned dose level.
- The initial drug dose is 75 mg BID.
- The capsules will be taken on an empty stomach (*i.e.* either 1 hour before or 2 hours after meals).
- On the days of radiation therapy, the daily dose will be administered within 30 min - 2 hours prior to radiation and can be taken at home if timing allows.
- Assessment of compliance with treatment: Patients will be instructed to keep a medication log, recording the date, time and numbers of capsules of each dose (See Appendix D)

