11. STUDY CALENDAR

Baseline evaluations are to be conducted within 1 week prior to start of protocol therapy. Scans and X-rays must be done \leq 4 weeks prior to the start of therapy. In the event that the patient's condition is deteriorating, laboratory evaluations should be repeated within 48 hours prior to

initiation of the next cycle of therapy.

NCI Protocol #: 10410
 Version Date: June 2, 2022

	Pre-Study	Wk 1	Wk 2	Wk 3	Wk 4	Wk 5	Wk 6	Wk 10 (4 wks following chemoRT) End of study for toxicity assessment	Wk 14-18 (8-12 wks following chemoRT) End of study for response assessment
IPdR		A	A	A	A	A	A		
Capecitabine		B	B	B	B	B	B		
Radiation therapy		C	C	C	C	C	C		
Surgical resection									X
mFOLFOX6 × 8 cycles	X								
Informed consent	X								
Demographics	X								
Medical history	X								
Concurrent meds	X	X	X	X	X	X	X	X	X
Physical exam	X	X	X	X	X	X	X	X	X
Vital signs	X	X	X	X	X	X	X	X	X
Height	X								
Weight	X	X	X	X	X	X	X	X	X
Performance status ^a	X	X				X		X	X
CBC w/diff, plts	X	X	X	X	X	X	X	X	X
Carcinoembryonic Antigen (CEA)	X							X	X
Comprehensive Chemistry Panel ^b	X	X	X	X	X	X	X	X	X
EKG (as indicated)	X								
Blood draws for PK and IUDR incorporation in granulocyte assays (mandatory)			X ^{c,d}	X ^{c,d}		X ^{c,d}			
Adverse event evaluation		X	X	X	X	X	X	X	
Radiologic evaluation	X								X ^e
Digital rectal exam and proctoscopic or sigmoidoscopic exam									X ^e
Pregnancy test ^f	X								

A: IPdR: Dose as assigned; PO QD administered throughout radiation (38 days, 6 weeks)
 B: Capecitabine: 825 mg/m² PO BID on days of radiation therapy (taken Monday morning through Friday evening each week of RT)
 C: Radiation therapy: 1.8 Gy/day × 28 doses (50.4 Gy total dose), M-F Days 1-5, 8-12, 15-19, 22-26, 29-33, 36-38
 a: Performance status evaluations are to be conducted every 4 weeks.
 b: Albumin, alkaline phosphatase, total bilirubin, bicarbonate, BUN, calcium, chloride, creatinine, glucose, LDH, magnesium, phosphorus, potassium, total protein, SGOT [AST], SGPT [ALT], sodium.
 c: 10 mL Blood for PK studies in sodium heparin tubes will be drawn on Day 8, prior to IPdR dose; and then after IPdR dose at 30 min, 60 min, 120 min and 240 min. On Day 21 and Day 35, blood will be drawn at 1-2 hours after the IPdR dose.
 d: 5 mL blood for measuring IUDR incorporation in granulocytes will be drawn in EDTA tubes prior to IPdR dose on Day 8, and at 1-2 hours after the IPdR dose on Day 21 and Day 35.

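### Section 7.2.2: the ten-dose count for the 5-day IPdR extension is wrong for once-daily Part IB, and no rule says what happens when radiation outlasts the extension

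*Combined protocol and SAP*

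**What the plan says.** Section 7.2.2 covers both once-daily and twice-daily IPdR, taken seven days a week. It sets three conditions on stopping:

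- The extension is limited: "Patients may receive up to 5 additional days (10 doses) of IPdR to accommodate delays in radiation therapy".
- Stopping is tied to the end of radiation, since IPdR is "to be discontinued only following the final dose of radiation therapy".
- The same point is then repeated for both schedules, where dosing "will continue through the last dose of radiation therapy".

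The schedule now in use is once daily. Section 6.1.1 states "Part IA is closed to further accrual", section 6.1.2 gives "once daily for Part IB (Week 6") and footnote A of the study calendar (section 11) gives "PO QD administered throughout radiation (38 days, 6 weeks").

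On radiation delay, section 7.2 says "Any missed radiation treatments will be made up at the end of the treatment schedule", so that the total stays at 28 fractions, and "A minimum of 4 daily radiation therapy treatments are required in any given week". It also keeps IPdR going while radiation is held, unless contraindicated, and lets the radiation oncologist hold radiation for toxicity and decide when to restart.

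The IPdR diary in Appendix D tells the patient to take the drug daily until radiation is finished. It mentions no cap, and its rows end at Day 38.

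**The concern.** There are two separate defects in one live dosing instruction for the investigational drug.

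First, the days and the doses in the cap sentence agree only for the closed schedule. Every patient still being accrued is on once-daily dosing, for which the two limits differ by a factor of two.

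Second, the cap ends dosing after a fixed extension, while the sentences around it tie the end of dosing to the last fraction. Once that fraction falls beyond the cap, a site cannot satisfy both as written. One site could stop at the cap and another could dose to fraction 28. Patients at the same dose level would then have different total exposure. Because section 6.2 captures DLTs until 4 weeks after IPdR ends, the close of the DLT window would move as well.

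**Working it through.** **Inputs.** Extension: 5 days, stated as 10 doses (7.2.2). Doses per day: 2 in Part IA, 1 in Part IB (6.1.2). Planned radiation: 28 weekday fractions, Day 1 a Monday, the last on Day 38 (study calendar, footnote C). Missed fractions are added at the end (7.2). IPdR is taken seven days a week, including while radiation is held (7.2, 7.2.2).

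**Dose count.** Doses = days × doses per day.

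- Twice daily: 5 × 2 = 10. This reproduces the plan's figure.
- Once daily: 5 × 1 = 5. The plan's figure does not hold.

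**Where the cap falls.** The term for the extra days is not defined, so two readings are possible.

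- Calendar days: 38 + 5 = Day 43.
- Radiation weekdays: the five weekdays after Day 38 are Days 39, 40, 43, 44 and 45, so the cap is Day 45. These span 45 − 38 = 7 calendar days, which is 7 once-daily or 14 twice-daily doses. Neither is 10, so the plan's own count favors the calendar-day reading.

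**Where the last fraction falls.** With *m* missed fractions, radiation ends on the (28 + *m*)th weekday.

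| Missed | Last fraction | Days after Day 38 | Past Day 43 cap | Past Day 45 cap |
|---|---|---|---|---|
| 1 | Day 39 | 1 | no | no |
| 2 | Day 40 | 2 | no | no |
| 3 | Day 43 | 5 | no | no |
| 4 | Day 44 | 6 | 1 day | no |
| 5 | Day 45 | 7 | 2 days | no |
| 6 | Day 46 | 8 | 3 days | 1 day |
| 7 | Day 47 | 9 | 4 days | 2 days |
| 8 | Day 50 | 12 | 7 days | 5 days |

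The calendar-day conflict starts at the fourth missed fraction and the weekday conflict at the sixth. For starts on other weekdays, counting from that schedule's own planned last fraction, the calendar-day conflict starts at the fourth or fifth.

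**Do such delays occur within the protocol's rules?** Yes, in two ways.

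- *Four fractions every week, no toxicity hold.* Six weeks give 6 × 4 = 24 fractions, and the remaining 4 fall in the week of Days 43–47. The last is on Day 47, or on Day 46 if Friday is the day missed each week. No pattern with at most one missed weekday per week ends later than Day 47.
- *Toxicity holds.* Section 6.2 counts a radiation interruption caused by an adverse event as a DLT above 5 consecutive or at 9 or more total scheduled fractions. Eight missed fractions with no run longer than 5 stay below that limit and end on Day 50.

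**The case against.** The best defense is that the number of days is the operative limit and the dose count is only a gloss, correct for twice-daily dosing and left over from Part IA. A once-daily site that follows the days stops after five. This stands in part: the figure is not an arithmetic slip for the schedule it came from. It is still wrong for everyone now accruing.

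A second defense is that the cap is the later and more specific sentence, so it qualifies the general continuation rule. That is a possible reading, but 7.2.2 says without exception that dosing stops only after the final fraction, the diary agrees, and nothing ranks the two. Missing precedence is a fair description of the second defect.

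A reader might go further in three ways that the documents do not support.

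- *That a site counting ten once-daily doses would dose to Day 48 as a matter of course.* Although 38 + 10 = 48, 7.2.2 ends IPdR at the last fraction. Day 48 is a Saturday on this calendar, and the four-per-week pattern ends by Day 47. Dosing on Day 48 needs radiation to run to Day 50 or later, which requires a longer hold.
- *That Day 47 is a ceiling*, making the excess at most 47 − 43 = 4 doses (47/43 = 1.093, or 9.3% more) on the calendar reading, or 47 − 45 = 2 days on the weekday reading. These maxima hold only if the weekly minimum is always met; toxicity holds can exceed them.
- *That IPdR should stop at the cap.* The schema, 6.1.1, study calendar footnote A and 7.2 all describe dosing for as long as radiation lasts. Stopping a radiosensitizer before radiation ends is a clinical choice that the documents do not make.

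**Conclusion.** Both defects hold. The ten-dose count is right only for the closed twice-daily part; for Part IB it should be five. The cap and the continuation rule agree for one to three missed fractions on a Monday start. They conflict from the fourth on the calendar-day reading (Day 44 against Day 43), or from the sixth on the radiation-weekday reading (Day 46 against Day 45).

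The size is a few daily doses. On the calendar reading it is 1 to 4 doses beyond the cap while every week has at least four fractions, and more with toxicity holds (50 − 43 = 7 at eight missed fractions). These counts assume a Monday start and uninterrupted IPdR. The documents do not say how often delays of four or more fractions occur, so no frequency is claimed. Severity is minor; no sample size or power figure is affected.

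**What to change.** In 7.2.2, change the cap to read: *up to 5 additional calendar days (5 doses if once daily; 10 doses if twice daily)*. Then have the sponsor state in the same paragraph which rule prevails when radiation runs past the cap.

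- **If the cap prevails:** qualify the two continuation sentences in 7.2.2; the wording in the schema, the 6.1.1 dose table and study calendar footnote A that ties IPdR to the whole of radiation; the statement in 7.2 that IPdR goes on while radiation is held; and the diary instruction. Extend the diary to Day 43 (43 − 38 = 5 more rows).
- **If continuation prevails:** delete the cap and keep the diary instruction. Add diary rows to cover the actual last fraction, not a fixed Day 47, which would be too short after a longer hold.

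The cost is amendment wording and some diary rows. No patients, visits or assays are added.

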7.3 IPdR and Capecitabine treatment management

Capecitabine and IPdR dose modifications are detailed in Table 7 and Table 8.

Additionally, the following dose modification instructions must be followed:

- All dose modifications should be based on the AE requiring the greatest dose modification.
- If RT is not administered (holiday, weekend, RT related toxicity, *etc.*), capecitabine is held; however, IPdR and RT continue per protocol unless otherwise contraindicated.
- If capecitabine and/or IPdR are held or discontinued, RT continues per protocol unless otherwise contraindicated.
- Capecitabine doses that have been reduced may not be escalated.
- IPdR doses that have been reduced may not be escalated.

Table 7: Capecitabine and IPdR dose levels

	Dose Level 0 Starting Dose (mg/m²)	Dose Level -1 (mg/m²)	Dose Level -2 (mg/m²)	Dose Level -3
Capecitabine	825 (BID) on days when RT is given	620 (BID) on days when RT is given	465 (BID) on days when RT is given	Discontinue
	Dose Level 0 Starting Dose	Dose Level -1	Dose Level -2	Dose Level -3

	Dose Level 0 Starting Dose (mg/m²)	Dose Level -1 (mg/m²)	Dose Level -2 (mg/m²)	Dose Level -3
IPdR	Part IA: Assigned dose level Part IB: see Table 6	Decrease one dose level (minimum dose is 75 mg QD; subjects requiring further dose reduction must have IPdR discontinued) See Tables 5 and 6 for Parts IA and IB dose levels	Decrease one dose level (minimum dose is 75 mg QD; subjects requiring further dose reduction must have IPdR discontinued) See Tables 5 and 6 for Parts IA and IB dose levels	Decrease one dose level (minimum dose is 75 mg QD; subjects requiring further dose reduction must have IPdR discontinued) See Tables 5 and 6 for Parts IA and IB dose levels

Table 8: Treatment management for capecitabine and IPdR

Important table instructions:

- Hold capecitabine and IPdR doses until any AE requiring dose modification returns to \leq grade 1 unless indicated otherwise in the treatment management sections/tables. If recovery to \leq grade 1 (or to other level specified) has not occurred after 3 weeks of delay, study therapy must be discontinued.
- All modifications in dose levels apply to both capecitabine and IPdR unless otherwise noted.

CTCAE v5.0 Adverse Event/Grade	Modifications for AEs that REQUIRED DELAY IN TREATMENT
Neutrophil count decreased: Grade 2 (1000- 1199/mm ³), 3, and 4	Hold capecitabine until \geq 1200/mm ³ . If recovery takes: 1 wk – maintain dose; 2-3 wks – \downarrow one dose level
Platelet count decreased: Grades 2, 3	Hold until \geq 75,000/mm ³ . If recovery takes: 1 wk – maintain dose; 2-3 wks – \downarrow one dose level
Grade 4	Hold until \geq 75,000/mm ³ . \downarrow one dose level

Important table instructions:

- Hold capecitabine and IPdR doses until any AE requiring dose modification returns to \leq grade 1 unless indicated otherwise in the treatment management sections/tables. If recovery to \leq grade 1 (or to other level specified) has not occurred after 3 weeks of delay, study therapy must be discontinued.
- All modifications in dose levels apply to both capecitabine and IPdR unless otherwise noted.

CTCAE v5.0 Adverse Event/Grade	Modifications for AEs that REQUIRED DELAY IN TREATMENT
GI : Diarrhea (despite optimal antidiarrheal management) Grades 2, 3	Treatment must be held for grades 2 and 3 diarrhea to avoid severe complications. 1 st occurrence – ↓ one dose level 2 nd occurrence – ↓ one dose level 3 rd occurrence – Discontinue
Grade 4	Discontinue
Mucositis - oral Grade 2	Maintain dose or ↓ capecitabine one dose level
Grade 3	↓ capecitabine one dose level
Grade 4	Discontinue capecitabine
Vomiting (despite antiemetics) Grades 2, 3	Hold and delay until \leq grade 1, then ↓ one dose level
Grade 4	↓ one dose level
Investigations (hepatic): Bilirubin, AST, alk phos Grades 2, 3	Hold until bilirubin returns to the baseline grade and AST and alk phos have returned to \leq grade 1; then ↓ one dose level
Grade 4	Discontinue chemotherapy
Febrile neutropenia: Grade 3	Hold until clinical resolution, then ↓ one dose level
Grade 4	Discontinue chemotherapy
Infection: Grade 2	Maintain dose or ↓ one dose level
Grade 3	↓ one dose level
Grade 4	↓ one dose level or discontinue
Nervous system disorders: Seizure Grades 1, 2, 3, 4	Any event of seizure, regardless of grade or attribution, requires discontinuation of IPdR and discussion with the PI regarding the decision to resume treatment.

Important table instructions:

- Hold capecitabine and IPdR doses until any AE requiring dose modification returns to \leq grade 1 unless indicated otherwise in the treatment management sections/tables. If recovery to \leq grade 1 (or to other level specified) has not occurred after 3 weeks of delay, study therapy must be discontinued.
- All modifications in dose levels apply to both capecitabine and IPdR unless otherwise noted.

CTCAE v5.0 Adverse Event/Grade	Modifications for AEs that REQUIRED DELAY IN TREATMENT
Skin and subcutaneous tissue disorders: Palmer-planter erythrodysesthesia syndrome Grades 2, 3	1 st occurrence – ↓ capecitabine one dose level 2 nd occurrence – ↓ capecitabine one additional dose level 3 rd occurrence – discontinue capecitabine
Other clinically significant AEs: * Grade 2	Maintain dose or ↓ attributable agent one dose level
Grade 3	↓ attributable agent one dose level
Grade 4	Discontinue attributable agent

* Determination of "clinically significant" AEs is at the discretion of the PI

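### Table 8 holds only capecitabine for neutropenia, an unexplained exception to its two-drug default; read literally, full-dose IPdR continues through afebrile grade 4 neutropenia

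*Combined protocol and SAP*

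**What the plan says.** Two default rules stand above Table 8 in Section 7.3. The first concerns holds: "Hold capecitabine and IPdR doses until any AE requiring dose modification returns to" grade 1 or better, unless the treatment management sections or tables indicate otherwise. The second concerns reductions: "All modifications in dose levels apply to both capecitabine and IPdR unless otherwise noted".

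The neutrophil row gives one instruction for grades 2, 3 and 4: "Hold capecitabine until" ANC is at least 1200/mm³. The dose is then maintained if recovery takes 1 week and reduced one level if it takes 2-3 weeks. The platelet row and the grade 3 febrile neutropenia row ("Hold until clinical resolution", then one level down) name no drug, so the two-drug default governs them.

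Three other statements bear on IPdR during neutropenia:

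- Section 7.2 makes an RT hold optional: "Radiation may be held for grade 3 dermatitis radiation, grade 4 neutropenia" and other listed toxicities. It also states: "If radiation is held, capecitabine will also be held; however, treatment with IPdR will continue unless otherwise contraindicated".
- A Section 7.3 bullet says that when RT is not given, "capecitabine is held; however, IPdR and RT continue per protocol unless otherwise contraindicated".
- Section 7.2.2 says that during an RT hold "IPdR continues unless criteria for dose adjustment is met per Section 6.2". Section 6.2 lists ANC below 500 among the DLTs, gives no dose-adjustment rule, and sends the reader to Section 7 for dose modifications.

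**The concern.** IPdR is the drug being escalated. Grade 4 neutropenia is a DLT (Section 6.2) and growth factors are barred (Section 6.4.1). The IPdR risk list in Section 10.1.1 says that the side effects of oral IPdR may resemble those of intravenous IUDR, and it names decreased neutrophil count among them. It also warns that IPdR may worsen events known from a partner drug, and Section 10.1.2 lists neutropenia for capecitabine. A reader would therefore expect a clear instruction for IPdR once ANC falls below 500, and the table does not give one.

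Two things are at stake. The first is the safety of the individual patient, who under the literal row keeps taking full-dose IPdR at that count. The second is consistency: one site may follow the row and another the header, so IPdR exposure could differ between patients at the same dose level in cohorts of 3 to 6.

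**Working it through.** The plan states no figure on this point, so there is none to reproduce. The check is a comparison of the texts, followed by dose counts from the study calendar.

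**Step 1. Rows side by side (Table 8).**

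| Event | Drug named in the hold | IPdR under the header default |
|---|---|---|
| Platelets, grades 2-3 and 4 | none | held |
| Febrile neutropenia, grade 3 | none | held |
| Diarrhea, vomiting, hepatic, grades 2-3 | none | held |
| Neutrophils, grades 2-4 | capecitabine only | continues if the row overrides; held if it does not |

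The mucositis and hand-foot rows name capecitabine and the seizure row names IPdR, but those rows reduce or discontinue a drug. The neutrophil row is the only hold instruction in the table that names a single drug. Read literally, it has two odd consequences:

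- Grade 2 thrombocytopenia interrupts IPdR, while afebrile ANC below 500 does not.
- The row's reduction after a 2-3 week recovery names no drug and so applies to both. IPdR would be given in full through the nadir and cut afterwards.

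**Step 2. Does another section close the gap?** Sections 7.2 and 7.3 continue IPdR when RT is held, subject to a contraindication that is not defined for neutropenia. Section 7.2.2 points to 6.2, and 6.2 points back to Section 7. One can read 7.2.2 as stopping IPdR at grade 4 because 6.2 lists ANC below 500, but that applies only when RT is held, and holding RT is optional.

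**Step 3. Size of the difference.** IPdR is daily on Days 1-38, so 38 doses. Per footnote C of the study calendar (Section 11), RT falls on Days 1-5, 8-12, 15-19, 22-26, 29-33 and 36-38. That is 28 days and 56 capecitabine doses. Assume RT continues on schedule and the hold starts on an RT day.

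| Hold | IPdR doses at issue | IPdR left if held | Capecitabine left |
|---|---|---|---|
| 7 days | 7/38 = 18.4% | 31/38 = 81.6% | 46/56 = 82.1% |
| 8 days | 8/38 = 21.1% | 30/38 = 78.9% | 44/56 = 78.6% |
| 14 days | 14/38 = 36.8% | 24/38 = 63.2% | 36/56 = 64.3% |
| 21 days | 21/38 = 55.3% | 17/38 = 44.7% | 26/56 = 46.4% |

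Each row covers the whole hold until ANC reaches 1200, including recovery through grades 3 and 2. The number of doses taken while ANC is below 500 is smaller, by an amount that the documents do not allow one to calculate.

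**Step 4. Would a grade 4 IPdR hold disturb the decision rules?**

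- *DLT count.* A treatment-related grade 4 event is already a DLT, so falling below 67% of intended IPdR (also a DLT under 6.2) adds nothing.
- *80% rule for the RP2D (Section 6.3), if it counts IPdR.* The possible single holds that start on RT day s and end by Day 38 number Σ(39 − s) = 28 × 39 − 536 = 556, where 536 is the sum of the RT day numbers. In none of them is IPdR below 80% while capecitabine is at 80% or more. That happens only for holds of 8-9 days starting on a weekend (10 capecitabine doses missed, so 46/56 = 82.1%; IPdR 30/38 = 78.9% or 29/38 = 76.3%).
- *Number of patients.* The dose taken forward allows at most 1 DLT in 6, so at least 5/6 = 83.3% are unaffected. The rule could tip only if another patient is below 80% for a different reason (4/6 = 66.7%).

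**Step 5. Why not hold IPdR at grades 2-3 as well?** Holds on Days 8-14 and 26-31 miss 10 + 8 = 18 capecitabine doses. The first run is 10 consecutive doses and the total is 18, both inside the interruption limits of Section 6.2 (more than 10 consecutive, or 19 in total). IPdR would fall to (38 − 7 − 6)/38 = 25/38 = 65.8%, a new DLT under the 67% rule. A hold at those grades would therefore be a real trade-off.

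**The case against.** A reader might infer that the header and the row contradict each other. They do not. The header allows exceptions, other rows use single-drug wording, and a capecitabine-first hold may be intended. That part of the defense stands.

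A reader might also infer that nothing but animal work supports continuing IPdR. The documents offer more. On the preclinical side, marrow and gut incorporation was 2-3 fold lower than with infused IUDR (Section 2.2.1.2), and rats showed no significant myelosuppression (Section 2.5.4). The human grade 4 neutropenia cited in 2.5.4, in 2 of 6 patients, came from continuous-infusion IUDR, not oral IPdR. On the human side, 28 days of oral IPdR with RT was judged tolerable (Section 2.2.1.3), and Section 2.4 relies on that profile. The study of IUDR with a fluoropyrimidine found no change in granulocyte incorporation and suggested only additive effects (Section 2.4.2). The body of Table 4, from the earlier IPdR trial, was not available for this check and may add to this. The evidence supports letting IPdR run at grades 2-3. None of it tests ANC below 500 on IPdR plus capecitabine plus pelvic RT.

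Existing safeguards also count: weekly blood counts, notification of DLTs to the Principal Investigator, and discontinuation for unacceptable AEs (Section 6.5). They permit an IPdR hold but do not require one.

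**Conclusion.** The point holds as an unexplained exception in a safety instruction that sites can apply in two ways. It is a cheap improvement, not an error that undermines the design. The readings differ by up to 7, 14 or 21 of 38 IPdR doses for holds of 1, 2 or 3 weeks.

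Two stronger readings should be resisted. The 21 doses (55%) are not doses given at ANC below 500; they are an upper bound over a hold running to the 3-week limit. Nor does the ambiguity at grade 4 distort dose escalation, because a treatment-related case is already counted as a DLT.

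The conclusion rests on the nominal calendar with RT continuing, on grade 4 neutropenia being attributed to treatment, and on six patients at the dose taken forward. How often afebrile grade 4 neutropenia will occur is not given. That a grade 4 hold is preferable is a safety judgment; the documents do not prove it is required.

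**What to change.** Make these short edits in one amendment:

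1. Split the neutrophil row of Table 8. Grade 4: *hold capecitabine and IPdR until ≥1200/mm³*, keeping the present 1-week and 2-3-week recovery rules. Grades 2-3: keep the capecitabine hold and add *IPdR continues*.
2. In Section 7.2, add that IPdR is also held when RT is held for grade 4 neutropenia.
3. In Section 7.2.2, replace the reference to Section 6.2 with one to Section 7.3, Table 8.

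The cost is some IPdR doses lost in a patient who is already a DLT if the event is treatment-related. No extra visits or tests are needed, since blood counts are already weekly. DLT counts and escalation stay as they are, and the 80% RP2D rule is exposed only in the case shown above, where another patient is also below 80%. If the sponsor does intend IPdR to continue at grade 4, one sentence saying so, with the reason, would remove the ambiguity; the reference in 7.2.2 would still need correcting.
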